15.8 MISSING DATE INFORMATION FOR ADVERSE EVENTS

Partial adverse event onset date will be imputed as follows: 1) if day is missing but month is not, impute the date as the first day of the month; 2) if both day and month are missing, impute the date as 01 Jan; 3) if imputed onset date is before the first treatment, yet the corresponding adverse event was not observed pre-treatment, then impute the onset date as the first treatment date. Imputed partial adverse event onset date will only be used to determine the adverse event onset cycle.

[figure not shown]
Other partial adverse event dates will not be imputed. All partial dates will be listed “as is” in the data listings.

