- During the retreatment period (from Day 180 through Day 330), participants who meet retreatment criteria will receive up to 2 blinded interventions of the same study intervention received in the first period (MT10109L 20 U, 44 U, or placebo).
[REDACTED]
- Participants who complete the study will have an exit visit at Day 360.
[REDACTED]

MT10109L

Number of Participants:

Approximately 375 participants will be enrolled in order to have 318 participants complete the study based on an anticipated dropout rate of 15%.

Number of Sites:

Approximately 16 global sites

Intervention Groups and Study Duration:

- The total duration of study participation for each participant is approximately 12 months (Day 1 randomization/treatment to end of study/Day 360). Participants will attend the following visits:
 - Screening (up to 28 days before Day 1)
 - Randomization and treatment (Day 1)
 - Follow-up visits on Days 7 and 14 after each intervention
 - Monthly (Days 30, 60, 90, 120, 150, 180, 210, 240, 270, 300, and 330)
 - Exit (Day 360 [completion] or early exit)
- On Day 1, participants will receive intramuscular injections of MT10109L 20 U (MT10109L in GL area, placebo in LCL area), MT10109L 44 U (20 U in GL area and 24 U in LCL area), or placebo (placebo in both GL and LCL areas).
- During the retreatment period (from Day 180 through Day 330), participants who meet retreatment criteria will receive up to 2 blinded interventions of the same study intervention received in the first period (MT10109L 20 U, 44 U, or placebo).

Data Monitoring Committee: No

Approval Date: 30-Sep-2020 22:55:16 (GMT)

2. Introduction

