6.1.2. Instructions for Use and Administration

Only trained and medically qualified physicians experienced with BoNT/A injections are authorized to administer the study interventions.

There will be up to 3 interventions in the study. In the first treatment period (Day 1 to at least Day 180), all participants will receive blinded intervention on Day 1, either MT10109L 20 U, 44 U, or placebo. In the retreatment period (from Day 180 through Day 330), all participants will

CONFIDENTIAL

Protocol MT10109L-005 AMD 4

[figure not shown]
MT10109L

receive MT10109L

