11.1 ADVERSE EVENTS

AEs will be coded from the verbatim text into preferred term (PT) and the primary system organ class (SOC) by using the MedDRA dictionary. In general, adverse events (AEs) data will be analyzed and presented for:

1. TEAEs: An adverse event will be considered a treatment-emergent adverse event (TEAE) if: 1) The adverse event began on or after the date of the first study intervention; or 2) The adverse event was present before the date of the first study intervention, but increased in severity or became serious on or after the date of the first study intervention. An adverse event that occurs more than 30 days after the study exit will not be counted as a TEAE.

[REDACTED]

Per case report form instructions, a new AE record will be created with a new AE onset date for any AE that worsens. Therefore, TEAEs can simply be identified as those AEs with a recorded onset date on or after the date of the first study intervention and within 30 days after the study exit.

In each of the analysis periods (entire study, or by treatment cycle), a specific TEAE will only count once per participant, associated with its worst severity during the time period of interest. Unless stated otherwise, the method of analyses described in this section will be applied to each of the screening/baseline and study intervention periods.

Adverse events will be summarized by treatment group for the entire study and by treatment cycle in descending order of incidence rate.

Three incidence rate tables will be presented for summarizing all TEAEs:

- 1) by descending order of incidence rate
- 2) by primary SOC and PT
- 3) by SOC, PT, and severity.

Serious TEAE and treatment-related TEAE will be summarized by primary SOC and PT for entire study. Treatment-related TEAE will also be summarized by related to study drug or related to study procedure. TEAE leading to study discontinuation will be summarized by primary SOC and PT for entire study

A participant listing will be generated for all AEs, SAEs, treatment-related AEs and AEs leading to study discontinuation.

All AEs associated with PDSOT will be tabulated by SOC, PT, and treatment group; in addition, all PDSOT AEs will be listed by participant.

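### SAP 15.8 protects only the first treatment when it imputes partial AE onset dates, so some partial-date AEs that follow a retreatment are counted in an earlier cycle

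*SAP*

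**What the plan says.** SAP 15.8 gives three numbered rules for a partial AE onset date.

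1. Day missing: "if day is missing but month is not, impute the date as the first day of the month".
2. Day and month missing: "if both day and month are missing, impute the date as 01 Jan".
3. The only correction has this condition: "if imputed onset date is before the first treatment, yet the corresponding adverse event was not observed pre-treatment". When it is met, the onset moves forward to the day of Treatment 1. Treatments 2 and 3 are not mentioned.

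It then limits the use of the result: "Imputed partial adverse event onset date will only be used to determine the adverse event onset cycle".

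That cycle feeds SAP 11.1: "Adverse events will be summarized by treatment group for the entire study and by treatment cycle in descending order of incidence rate". Within each analysis period, SAP 11.1 counts a given event once per participant.

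There can be three cycles. Protocol 6.1.2 states: "There will be up to 3 interventions in the study". The Synopsis (Protocol 1.1) adds: "During the retreatment period (from Day 180 through Day 330), participants who meet retreatment criteria will receive up to 2 blinded interventions". Nothing ties a retreatment to the start of a month.

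**The concern.** The rule exists to choose a cycle, but it ignores the dates on which cycles 2 and 3 begin. It picks the earliest date that fits the known parts. That date can fall before a retreatment even when the event came after it, and rule 3 does nothing unless the date also falls before the first treatment.

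The by-cycle AE summaries are the visible analysis that separates AEs after retreatment from AEs after the first injection. Protocol 4.1.1 includes acceptable safety after single treatment and retreatments among its clinical hypotheses. An error that only moves events out of cycles 2 and 3 makes retreatment look safer than it was. A moved event can also vanish from the by-cycle counts: if the participant already had the same event in the earlier cycle, the once-per-period rule absorbs it.

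The direction is also out of step with neighbouring conventions. SAP 15.6 treats missing severity after the first dose as severe, and SAP 15.7 treats missing causality as related. Rule 3 itself assigns doubtful onsets to the first treatment. Each of these leans against the product. The handling of retreatments leans the other way.

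**Working it through.** The plan gives no misassignment figure to reproduce, so this check applies the rule as written.

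**Inputs and assumptions.** The three rules come from SAP 15.8. Up to three treatments, with retreatment between Day 180 and Day 330, come from Protocol 6.1.2 and 1.1. The illustrative Day 1 of 29 August 2018 comes from SAP 15.9. Assumed: the cycle is set by the latest treatment on or before the onset date, an AE on the treatment day belongs to the new cycle, treatment dates spread evenly over the calendar, and lags after retreatment are uniform over the stated range. Where dates of both retreatments are needed, Day 180 and Day 330 are used.

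**Worked example.** 29 August 2018 + 179 days = 24 February 2019 (Day 180). Adding 329 days gives 24 July 2019 (Day 330).

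| True onset | Known part | Imputed | True cycle | Assigned cycle |
|---|---|---|---|---|
| 26 Feb 2019, 2 days after Treatment 2 | Feb 2019 | 1 Feb 2019 | 2 | 1 |
| 3 Mar 2019, 7 days after Treatment 2 | Mar 2019 | 1 Mar 2019 | 2 | 2 (correct) |
| 26 Jul 2019, 2 days after Treatment 3 | Jul 2019 | 1 Jul 2019 | 3 | 2 |
| 26 Jul 2019, 2 days after Treatment 3 | 2019 | 1 Jan 2019 | 3 | 1 |

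**Day missing.** In a 30-day month with the retreatment on day r, an AE at lag L is misassigned if r + L ≤ 30 and r > 1. The share is (29 − L)/30 for L up to 29, and zero beyond. The last column repeats the check over every Day 1 in a four-year calendar.

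| Lag (days) | 30-day month | Real calendar |
|---|---|---|
| 0 | 29/30 = 96.7% | 97% |
| 7 | 22/30 = 73.3% | 74% |
| 14 | 15/30 = 50.0% | 51% |
| 29 | 0/30 = 0% | 2% |
| 0-13 | 315/420 = 75.0% | 75% |
| 0-29 | 435/900 = 48.3% | 49% |
| 0-149 | 435/4,500 = 9.7% | 10% |

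The 0-13 day figure can be split: 329/420 = 78.3% of onsets fall in the retreatment month, and 315/329 = 95.7% of those are misassigned.

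**Year only.** In a 365-day year the share is (364 − L)/365.

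- Lags 0-29 (mean 14.5): 349.5/365 = 95.8%; calendar 96%.
- Lags 0-149 after Treatment 2 (mean 74.5): 289.5/365 = 79.3%; calendar 79%.
- Two cycles back after Treatment 3: Treatment 2, 150 days earlier, must fall in the same year. Over lags 0-29 the share is (364 − 150 − 14.5)/365 = 199.5/365 = 54.7%; calendar 55%.

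**Direction.** No AE in the calendar check moved to a later cycle.

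**The case against.** The case against giving this much weight is about scope, and most of it stands.

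- **Few events may qualify.** The fault needs a retreated participant, a partial onset date, and an onset in the retreatment's own month (or year, if the month is unknown). Protocol 8.2.1 requires the onset date and asks about AEs since the previous visit. Visits fall 7 and 14 days after each intervention and monthly. Year-only dates should be rare. Every percentage above is conditional on a partial date, and the documents give no rate of partial dates.
- **Few tables are touched.** SAP 11.1 anchors treatment-emergent status on the first intervention and specifies the serious, treatment-related and discontinuation summaries for the entire study. The severity and causality rules are anchored on the first dose. None of these uses the imputed cycle.
- **All arms share the rule.** It does not favour one arm by design, though it can still dilute a difference between arms within a retreatment cycle.
- **Some text cannot be seen.** Parts of SAP section 15 are not in the public text, so the cycle definition is not visible. The numbered rule nevertheless reads as complete.

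Two stronger readings are tempting. One is that AEs after retreatment in general go to the previous cycle. They do not: complete dates are untouched, and the 3 March example is assigned correctly. The other is that, in the worked example, every AE dated only 2019 is an error. It is not: cycle 1 is right for onsets before 24 February 2019 and for anyone not retreated.

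These points limit the size. They do not remove the fault, because following the rule exactly gives a wrong cycle for a definable set of events, always in the same direction.

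**Conclusion.** The point holds within a narrow scope. As written, SAP 15.8 moves a day-missing AE backward when it follows a retreatment in the same month and the retreatment was not on the 1st. It moves a year-only AE backward when it follows a retreatment in the same year and the retreatment was not on 1 January.

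Among day-missing AEs, early post-injection events are hit hardest. The figures rest on evenly spread treatment dates and uniform lags. The absolute number of events cannot be estimated from the documents and may be small.

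A reader might infer that the overall safety conclusions or the total AE counts are understated. The documents do not support that: no event leaves the whole-study summaries, and efficacy is not involved. What is affected is the by-cycle AE description, where cycles 2 and 3 are understated and earlier cycles can be overstated. The correction is worth making because the bias is systematic and cheap to remove.

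**What to change.** **Day-missing dates.** Extend rule 3 to every treatment. If the reported month contains a retreatment and the AE was not recorded before it, impute the onset as that retreatment date. Do not do so if the AE stop date or the visit of first report shows that onset came earlier.

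**Year-only dates.** Assign the cycle from the visit at which the AE was first reported and from its stop date. Show any event that still cannot be placed as cycle unknown. Moving year-only dates to the latest compatible retreatment, with no other bound, would overcorrect. A cycle-1 AE would move forward whenever Treatment 2 fell in the same year. The mean gap to Treatment 2 over the 179 days of cycle 1 is 90 days, so the share is (365 − 90)/365 = 75.3%.

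**Reporting.** Footnote the by-cycle tables with the number of AEs whose cycle was imputed, so that the reader can judge the effect.

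**Cost.** A short SAP change and a small derivation change, using stop dates and visit information already collected. For day-missing dates, backward misassignment over lags 0-29 falls from about 49% to 0% before the bounds are applied. The price is that some true cycle-1 AEs in the month of Treatment 2 move forward. On average 14.5 days of that month precede the retreatment, so the share is 14.5/179 = 8.1% of day-missing cycle-1 AEs (calendar check 8%). The stop-date and first-report bounds should lower it, and what remains is conservative for retreatment safety.

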15.9 MISSING DATE INFORMATION FOR PRIOR OR CONCOMITANT MEDICATIONS

There will be no imputation for missing or partially reported medication start and/or end dates. However, reported partial information will be utilized in classification of prior and concomitant medications, when appropriate. For example, a medication may be classified as a pre-study medication if the partial end date provided is determined to definitively have occurred prior to the study intervention date (for example, the partial end date provided is “2017”, and Day 1 occurred on August 29, 2018).

If start and/or stop dates for medications are only partially reported but can be classified as having occurred prior to Day 1, then the medications will be included in this summary of prior medications.

If stop dates for medications are only partially reported and cannot be definitively classified as having occurred prior to Day 1, then the medications will be included in this summary of concomitant medications.

18.0 HISTORY OF CHANGES

Amendment 1:

Date	Section(s)	Description
11/1/2020	3.0	Added abbreviation AESI.
11/18/2020	4.0	Changed to base on protocol amendment dated Oct 2020.
11/1/2020	7.0	Deleted word “cumulative” to remove confusion.
11/1/2020		[REDACTED]
11/1/2020	11.1	Added summary for AESI.
11/1/2020	11.8	Added “Impact due to COVID-19” section.
11/1/2020		[REDACTED]
11/1/2020	15.2	Added data step in a specific scenario when value is not in range after iteration when conducting [REDACTED] Revised typo “BOTOX” to “MT10109L”. [REDACTED]
11/1/2020	15.4	Added detail about the calculation [REDACTED]
11/18/2020	16.0	Added [REDACTED]
11/18/2020	17.0	Added references.

Electronic Signatures
